11. STATISTICAL PLAN

11.0 Definitions

11.0.0 Participant Populations

For this trial the following populations will be defined and used in the analysis:

Intent-to-treat (ITT) Population

The Intent to Treat (ITT) population consists of all participants enrolled into the study.

Per-protocol Population

The PP population is defined as all participants recruited into the trial who received Investigational Medicinal Product and had no major protocol violations.

Safety Population

The safety population will include all participants in the ITT population.

Pharmacokinetic (PK) Population

The PK population will include all participants enrolled in this study who receive the IMP through to the morning dose of Visit 5 (Week 2) as a minimum, and who undergo PK sample collection at the specified post-dose time point(s) through to Visit 5 as a minimum.

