9.6 Pharmacokinetic Measurements

Pharmacokinetic blood samples will be collected in accordance with the sampling schedule outlined in Table 2 for ages 7 to 17 years old and Table 3 for ages 3 to < 7 years old. The date and actual time (hour and minute) that each sample is collected must be accurately recorded. The site must also ensure that the date and time of the previous evening's dose and the morning and evening dose on the day the sample is collected is accurately collected in the Caregiver Diary.

For the Week 2, 6, and 13 data collection, the previous day's PM dose should be taken in the evening as late as possible, preferably before bedtime. The pre-dose sample should be taken 120 minutes to 15 minutes before the morning dose is administered. For post-dose samples, sample collection can be \pm 15 minutes of the target time and must be no closer than 30 minutes from the previous sample (must be

at least 30 minutes from the previous sample). The actual collection time is recorded. The post-dose windows are determined from the first dose of the visit (morning dose) and all PK samples should be collected before the second dose (PM dose). Full details regarding the PK sampling collection, storage and shipping may be found in the Laboratory Manual for the study.

PK blood samples may be collected from a cannula port or via venipuncture. Pre-prepared PK sampling tubes will be provided to each site within the lab visit kits for collection and storage of PK samples. Samples of whole blood will be collected, aliquoted, and will be stored at minus 20° C (or colder) no more than 2 hours following sample collection. Samples will be shipped at designated times on dry ice and using temperature monitoring to the laboratory for storage and analysis. It is essential that accurate records are maintained regarding the date and time each PK sample is obtained, and the date and time each sample is placed in the -20° C freezer. The date and time of the most recent dose of IMP and most recent meal relative to that dose should be recorded in the Caregiver Diary.

Minimum requirements for a participant to be considered evaluable within the PK population are administration of NNZ-2591 per protocol through to the morning dose at Visit 5 (Week 2) as a minimum, and collection of PK samples at the specified post-dose time point(s) through to Visit 5 (Week 2) as a minimum.

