11.4 Pharmacokinetic Analysis

The PK analysis will be based on the endpoints listed in Section 6.3.1. Pharmacokinetic (PK) measures will be collected from all participants at Visits 5 (Week 2), 9 (Week 6), and 16 (Week 13, EOT).

NNZ-2591 PK concentrations will be listed by participant and time point for each dose level with actual time they were acquired. The concentrations will be summarized by time, dose level, and age group. For the concentrations measured at trough points dose relationship will be examined statistically with age group and/or body weight of participant as covariate.

Overall exposure parameters for NNZ-2591 such as C_{max} and AUC_{tau} may be derived by sparse non-compartmental analysis (NCA). Additionally, PK concentrations of NNZ-2591 measured in pediatric participants will be used to refine population PK model developed from adult NNZ-2591 PK data and extrapolated to pediatric population. After refinement, complete profiles for each participant will be simulated using range of variability of model parameters and individual covariate effects. A standard NCA approach will be used for simulated profiles to calculate parameters C_{max} , AUC_{tau} , etc. for characterization of NNZ-2591 exposure in pediatric participants.

The PK analysis details will be specified in the PK SAP.

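### Read literally, the PK population leaves out a child who misses post-dose sampling at Visit 5, however complete that child's samples are at the two later, higher-dose visits

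*Protocol*

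**What the plan says.** Protocol 11.0.0 opens its list of analysis sets with "For this trial the following populations will be defined and used in the analysis". The only PK set on that list has two conditions. The child must be one of those "who receive the IMP through to the morning dose of Visit 5 (Week 2) as a minimum", and one of those "who undergo PK sample collection at the specified post-dose time point(s) through to Visit 5 as a minimum".

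Protocol 9.6 states nearly the same rule as a test of evaluability: "Minimum requirements for a participant to be considered evaluable within the PK population are administration of NNZ-2591 per protocol" through the Visit 5 morning dose, together with "collection of PK samples at the specified post-dose time point(s) through to Visit 5 (Week 2) as a minimum". Neither section offers another way to qualify, and neither sets a rule for each visit or each parameter.

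Protocol 11.4 gives the visits: "Pharmacokinetic (PK) measures will be collected from all participants at Visits 5 (Week 2), 9 (Week 6), and 16 (Week 13, EOT"). It plans listings, summaries by time, dose level and age group, a trough analysis and a possible sparse NCA. It also says that the measured concentrations "will be used to refine population PK model developed from adult NNZ-2591 PK data and extrapolated to pediatric population". It names no population for any of these and leaves the details to a PK SAP. The main SAP (Section 3) defines ITT, Safety and mITT sets, has no PK set, and also refers PK to a separate plan.

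**The concern.** PK is part of the primary objective. Membership of the only PK set is decided entirely at the first PK visit, on the starting dose. A failed cannula or a refused draw on that day cannot be made good later. A child with full sampling at Visits 9 and 16 would still be outside the set, although those visits carry the information on the two higher dose levels.

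None of the analyses described in 11.4 needs complete Visit 5 data from a child before that child's later samples can be used. If the set is applied as written, usable concentrations are set aside for a reason unrelated to their quality. The study plans only 10 to 20 completers and allows as few as three children in an age group, so each such loss is noticeable.

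**Working it through.** **Inputs from the documents**
- PK visits: 5, 9 and 16 (Protocol 11.4).
- Scheduled dose: 4 mg/kg BID at Week 2, 8 mg/kg BID at Week 6, 12 mg/kg BID at Week 13 (Protocol 7.2, Table 4).
- Draws per visit: one pre-dose and two post-dose for ages 7 to 17 (Table 2); one pre-dose and one post-dose for ages 3 to under 7 (Table 3).
- Size: 10 to 20 completers, at least 3 per age group (Protocol Section 8).

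**Assumption, not in the documents:** the probability *p* that a single draw is missed. I use 5%, 10% and 20%.

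**Step 1. Reproduce the plan's sample counts.** Ages 7 to 17: 3 × (1 + 2) = 9. Ages 3 to under 7: 3 × (1 + 1) = 6. Both match the sample numbering in Tables 2 and 3.

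**Step 2. Samples left outside the set when one Visit 5 post-dose draw is missed and everything else is collected.**

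| | Visit 5 | Visit 9 | Visit 16 | Outside the set | Of these, at the two higher doses |
|---|---|---|---|---|---|
| Ages 7–17 | 2 | 3 | 3 | 8 of 9 | 6 |
| Ages 3 to <7 | 1 | 2 | 2 | 5 of 6 | 4 |

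If an older child misses both Visit 5 post-dose draws, 1 + 3 + 3 = 7 of 9 fall outside, again 6 of them at the higher doses. All of these are ceilings, because they suppose that nothing else is missed.

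**Step 3. Share of a group.** One child in a group of three is 1/3. One child overall is 1/10 = 10% or 1/20 = 5%.

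**Step 4. How often, for illustration only.** With independent draws, the chance of failing the rule is 1 − (1 − *p*)² for ages 7 to 17 and *p* for ages 3 to under 7. Call that chance *q*. The chance that a group of three loses at least one child is 1 − (1 − *q*)³.

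| *p* | *q*, ages 7–17 | At least 1 of 3 | *q*, ages 3 to <7 | At least 1 of 3 |
|---|---|---|---|---|
| 5% | 1 − 0.95² = 9.75% | 26.5% | 5% | 14.3% |
| 10% | 1 − 0.90² = 19% | 46.9% | 10% | 27.1% |
| 20% | 1 − 0.80² = 36% | 73.8% | 20% | 48.8% |

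If one cause spoils both draws together, *q* for the older children falls from 1 − (1 − *p*)² towards *p*. The last column supposes that all three children follow Table 3; a 7-year-old belongs to enrolment Group 3 but follows Table 2.

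**Step 5. What each planned analysis needs.** Summaries at the two higher dose levels need the draws from Visits 9 and 16. The trough analysis needs the pre-dose draw of the visit concerned. The population model can use any concentration with a known sample time and dose history. Sparse NCA pools concentrations across children. None of these needs a Visit 5 post-dose draw from a child as the price of using that child's later data.

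**The case against.** The strongest reply is that the rule may do little harm in practice. Section 11.2 ties the safety analyses to the Safety Population, but 11.4 ties no PK analysis to the PK population. Its wording speaks of participants in general, and the PK SAP may already set evaluability by visit or by parameter. A reader might infer that the excluded child is lost from every PK analysis, or that target-dose data will certainly be discarded. The documents do not establish that. It is a fair inference, because 11.0.0 says its populations are used in the analysis and offers only this PK set, but it remains an inference.

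Second, 11.0.0 does not say that all the specified post-dose points are required. For ages 7 to 17, two draws are scheduled, and the figure of 8 of 9 rests on reading the rule as both. That is the natural reading, since the optional plural fits two draws in older children and one in younger ones. For ages 3 to under 7 there is only one post-dose draw, so the doubt does not arise. A footnote to the tables lets the pre-dose sample stand also for 12 hours after the previous evening's dose. The tables and 9.6 nevertheless keep pre-dose and post-dose samples apart, so this does not rescue the child.

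Third, the miss rates are assumed, and the design has some protection: wide post-dose windows, a cannula or venipuncture, and a visit that may run over three days. This stands, and the rates in Step 4 should not be read as a forecast.

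Two further inferences should be resisted. A reader might call it a flaw that a child with no pre-dose sample still qualifies. That is no defect of membership: such a child adds nothing to the trough analysis but can still inform the model, and the definition proposed below admits the same child. Nor is the extra per-protocol dosing condition in 9.6 a serious conflict. It is a real difference from 11.0.0, but it needs only harmonising.

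**Conclusion.** The point holds as a defect in a stated definition. Taken literally, 11.0.0 and 9.6 make the starting-dose visit the sole entry to the only PK set, so a child with complete sampling at both higher doses can be outside it. This is certain for ages 3 to under 7 (up to 5 of 6 samples) and is the natural reading for ages 7 to 17 (up to 8 of 9). One exclusion can remove a third of the smallest permitted age group. Which analyses would suffer cannot be determined from these documents, and the frequency is unknown. Referral to a PK SAP does not remove the problem, because that plan must either follow the protocol's rule or override it. The change should be made; it does not call the study's design into question.

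**What to change.** Use one definition, word for word the same in Protocol 9.6 and 11.0.0, and carry it into the PK SAP: all participants who received at least one dose of IMP and have at least one evaluable concentration with a recorded sample time and a recorded time of the preceding dose. This also removes the difference over per-protocol dosing.

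Move completeness from the child to the visit and the parameter. A visit enters the trough analysis if its pre-dose sample is present. It enters an NCA summary if the samples which that parameter needs are present. State in the PK SAP which set each PK analysis uses.

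Under this rule the children in Step 2 would keep their 8 of 9 or 5 of 6 samples instead of none. The cost is about two sentences in the protocol, the matching text in the PK SAP, and no new data. The downside is that the number of children will differ between visits and summaries, so each table must show its own count.

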11.1 Sample Size Determination

Sample sizes were estimated for this open-label study using within-participant change as the measure of improvement. Given the limited data from interventional trials in these patient populations, and that this is the first clinical study for NNZ-2591 IMP in this population, treatment change estimates were based on Clinical Global Impression Scale of Improvement (CGI-I) data from completed clinical trials in other rare, neurodevelopmental disorders.

Based on the information provided in Glaze et al. 2019 (Double-blind, randomized, placebo-controlled study of trofinetide in pediatric Rett syndrome), the standard deviation of the CGI-I is approximately 0.7 at a single timepoint. For a sample size of 10 participants, a two-sided significance level of 0.05, and a Wilcoxon signed-rank test, the study will be able to detect a difference of 0.87 units of change in the CGI-I at a power of 0.90. For a power of 0.80, 0.85, and 0.90, the detectable difference would be 0.75, 0.80, and 0.87 or larger, respectively. The effect size for a power of 0.80, 0.85, and 0.90 is 1.07, 1.14, and 1.24, respectively. If the observed standard deviation is larger, the detectable differences would also be larger. For example, if the standard deviation is 1.5, the detectable difference for a power of 0.80, 0.85, and 0.90 is 1.61, 1.71, and 1.86 or larger, respectively. For a sample size of 20 participants, a two-sided significance level of 0.05, and a Wilcoxon signed-rank test, the study will be able to detect a difference of 0.55 units of change in the CGI-I at a power of 0.90. For a power of 0.80, 0.85, and 0.90, the detectable difference would be 0.48, 0.51, and 0.55 or larger, respectively.

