Sample sizes were estimated for this open-label study using withinparticipant change as the measure of improvement. Given the limited data from interventional trials in these patient populations, and that this is the first clinical study of NNZ-2591 IMP in this population, treatment change estimates were based on CGI-I data from completed clinical trials in other rare, neurodevelopmental disorders. Based on the information provided in Glaze et al. 2019 (Double-blind, randomized, placebo-controlled study of trofinetide in pediatric Rett syndrome), the standard deviation of the CGI-I is approximately 0.7 at a single timepoint. For a sample size of 10 participants, a two-sided significance level of 0.05, and a Wilcoxon signed-rank test, the study will be able to detect a difference of 0.87 units of change in the CGI-I at a power of 0.90. For a power of 0.80, 0.85, and 0.90, the detectable difference would be 0.75, 0.80, and 0.87 or larger, respectively. The effect size for a power of 0.80, 0.85, and 0.90 is 1.07, 1.14, and 1.24, respectively. If the observed standard deviation is larger, the detectable differences would also be larger. For example, if the standard deviation is 1.5, the detectable difference for a power of 0.80, 0.85, and 0.90 is 1.61, 1.71, and 1.86 or larger, respectively. For a sample size of 20 participants, a two-sided significance level of 0.05, and a Wilcoxon signed-rank test, the study will be able to detect a difference of 0.55 units of change in the CGI-I at a power of 0.90. For a power of 0.80, 0.85, and 0.90, the detectable difference would be 0.48, 0.51, and 0.55 or larger, respectively.

Statistical Methods

Safety

Adverse events and other safety data will be summarized as frequencies and percentages, described in terms of severity and potential attribution. Objective safety assessments will be summarized over time on study; shift tables at time points of interest may be generated. Details of the safety analyses will be specified in the SAP.

Efficacy

Efficacy will be assessed by looking at within-participant changes from the Baseline period to the EOT. The participant's baseline characteristics and symptom severity will be established based on assessments collected during the 4 to 6 week Screening/Baseline period. Baseline values will be based on the average values of visits 1, 2, and3 for assessments collected at more than one visit. A Wilcoxon

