signed rank test will be used to test for improvement and a significance level will be computed.

Potentially influential factors will be considered and addressed with a linear regression model. This model may include covariates such as age, sex, NVIQ or NVIQ equivalent, genotype, history of regression (yes/no), ASD diagnosis yes/no with no more than two covariates included in any model. Descriptive statistics and corresponding graphics will be used to present the results. The efficacy analysis details will be specified in the SAP.

Pharmacokinetics:

NNZ-2591 PK concentrations will be listed by participant and time point for each dose level with actual time they were acquired. The concentrations will be summarized by time, dose level and age group. For the concentrations measured at trough points dose, relationship will be examined statistically with age group and/or body weight of participant as covariate.

Overall exposure parameters for NNZ-2591 such as C_{max} and AUC_{tau} may be derived by sparse non-compartmental analysis (NCA). Additionally, PK concentrations of NNZ-2591 measured in pediatric participants will be used to refine a population PK model developed from adult NNZ-2591 PK data and extrapolated to the pediatric population. After refinement, complete profiles for each participant will be simulated using range of variability of model parameters and individual covariate effects. A standard NCA approach will be used for simulated profiles to calculate parameters C_{max}, AUC_{tau}, etc. for characterization of NNZ-2591 exposure in pediatric participants.

The PK analysis details will be specified in the PK Statistical Analysis Plan (PK SAP).

Biomarkers and Microbiome:

Biomarker analysis will be detailed in the SAP and will not include DNA sequencing.

Microbiome analysis will be described in a separate analysis plan.

Trial Sites

Approximately 4-7 sites in the US.

Neuren Pharmaceuticals Ltd.Clinical Trial ProtocolVersion 3.0ConfidentialNeu-2591-PTHS-001October 30, 2023

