7. STUDY DESIGN

7.1 Study Design Overview

This is a Phase 2, open-label study of the safety and tolerability of NNZ-2591 Oral Solution, 50 mg/mL in male and female children and adolescents with Pitt-Hopkins syndrome. Approximately 10 to 20 male and female participants between the ages of 3 and 17 years will be enrolled and receive treatment of NNZ-2591 Oral Solution, 50 mg/mL for a total of 13 weeks. Additional participants may be screened, enrolled, and treated to achieve approximately 20 study completers.

There will be a total of 17 study visits, comprising 5 in-clinic visits, and 12 remote telemedicine/in-home nurse visits. The study will commence with an approximately 4 to 6 week Screening and Baseline period. During this Screening/Baseline period, participants will be assessed for study eligibility and data will be collected to establish the participant's baseline characteristics and symptom severity using a variety of assessments (Section 9.2). Two in-clinic visits and one remote/in-home visit (Visits 1, 2, 3) comprise Screening and Baseline.

Once eligibility is confirmed, participants will receive the starting dose of 4 mg/kg and then be up-titrated to the target dose (see Section 7.2). Participants will receive treatment for a total of 13 weeks. During the treatment period, there are three in-clinic visits: Week 2 (Visit 5), Week 6 (Visit 9) and Week 13 (Visit 16). There is a combined remote, telemedicine visit by the site investigator and an in-home visit by a visiting nurse for safety at Week 1 (Visit 4), Week 4 (Visit 7), Week 8 (Visit 11) and Week 10 (Visit 13). These combination remote/in-home visits will be conducted simultaneously whenever possible, or they will be conducted on the same day with the telemedicine visit occurring first. If it is not feasible to conduct these visits simultaneously or on the same day, the telemedicine portion of the visit and the nurse portion of the visit must be conducted on two consecutive days. In-home visits with a visiting nurse will be done at Weeks 3 (Visit 6), 5 (Visit 8), 7 (Visit 10), 9 (Visit 12), 11 (Visit 14), and 12 (Visit 15).

All participants will also have a remote post-treatment visit with the Investigator via telemedicine and an in-person home visit by a visiting nurse approximately 2 weeks after the end of treatment (Week 15, Visit 17).

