11.3 Efficacy Analysis

Efficacy will be assessed by looking at within-participant changes from the Baseline period to the EOT using the efficacy endpoints listed in Section 6.3.2.

The participant's baseline characteristics and symptom severity will be established based on assessments collected during the 4 to 6 week Screening/Baseline period. Baseline values will be based on the average values of visits 1, 2, and 3 for assessments collected at more than one visit. A Wilcoxon signed rank test will be used to test for improvement and an exact significance level will be computed.

Potentially influential factors will be considered and addressed with a linear regression model. This model may include covariates such as age, sex, nonverbal NVIQ or NVIQ equivalent, genotype, history of regression (yes/no), ASD diagnosis (yes/no) with no more than two covariates included in any model. Descriptive statistics and corresponding graphics will be used to present the results. The safety and efficacy analysis details will be specified in the SAP.

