### 5.1 Determination of Sample Size

Sample sizes were estimated for this open-label study using within-subject change as the measure of improvement. Given the limited data from interventional trials in these patient populations and that this is the first clinical study of NNZ-2591 IMP in this population, treatment change estimates were based on Clinical Global Impression Scale of Improvement (CGI-I) data from completed clinical trials in other rare, neurodevelopmental disorders. Based on the information provided in Glaze et al. 2019 (Double-blind, randomized, placebo-controlled study of trofinetide in pediatric Rett syndrome), the standard deviation of the CGI-I is approximately 0.7 at a single timepoint. For a sample size of 10 subjects, a two-sided significance level of 0.05, and a Wilcoxon signed-rank test, the study will be able to detect a difference of 0.87 units of change in the CGI-I at a power of 0.90. For a power of 0.80, 0.85, and 0.90, the detectable difference would be 0.75, 0.80, and 0.87 or larger, respectively. The effect size for a power of 0.80, 0.85, and 0.90 is 1.07, 1.14, and 1.24, respectively. If the observed standard deviation is 1.5, the detectable difference for a power of 0.80, 0.85, and

0.90 is 1.61, 1.71, and 1.86 or larger, respectively. For a sample size of 20 subjects, a two-sided significance level of 0.05, and a Wilcoxon signed-rank test, the study will be able to detect a difference of 0.55 units of change in the CGI-I at a power of 0.90. For a power of 0.80, 0.85, and 0.90, the detectable difference would be 0.48, 0.51, and 0.55 or larger, respectively.

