### 5.3 Definitions

- Age will be derived as the integer value of (informed consent/assent date date of birth + 1)/365.25.
- The age at time of assessment will be derived as the integer value of (date of assessment date of birth + 1)/365.25.

- Body Mass Index (BMI) will be derived as weight in kilograms divided by height in meters squared.
- The change from Baseline measurement for a variable at a particular visit will be derived as the measurement taken at the specified visit minus the baseline measurement. For the Clinical Global Impression Scale Improvement and Caregiver Impression of Change, change from Baseline is the value at the visit.
- Treatment duration in days will be derived as follows: Date of Last Dose Date of First Dose + 1.
- The number of expected doses will be derived as (2\*treatment duration in days)-1, as subjects are expected to receive only their morning dose on the last day of treatment
- The number of doses taken will be derived as the number of doses taken as indicated by the Administration of First Dose CRF and by the Daily Dosing Log CRF for remaining doses, based on completed date and dose fields
- Number of missed doses will be derived based on the number of expected doses the number of doses taken
- Study Day will be derived as Date of Event Date of First Dose (+1 if the date of event ≥ date of first dose)
- Screening/baseline duration in days will be derived as follows: Date of First Dose Date of Screening
- Study duration will be defined as the total number of days in the study (date of last visit date of informed consent + 1).
- History of developmental regression will be determined from the PTHS diagnosis page of the CRF question: "Has the child undergone a regression of skills in the past?" If coded as "yes" the subject is considered as having had a past developmental regression.
- Autism Spectrum Disorder (ASD) diagnosis will be derived from the PTHS diagnosis page of the CRF. If ASD is checked under "confirmation of psychiatric co-morbidities", the subject is considered as having the disorder.
- Bipolar Disorder will be derived from the PTHS diagnosis page of the CRF. If "Bipolar disorders" is checked under "confirmation of psychiatric comorbidities", the subject is considered as having the disorder.

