#### 9.2.1 Clinical Global Impression Scale - Overall Improvement Score

CGI-I assessments are completed at Visit 9 (Week 6), End of Treatment (Week 13, Visit 16), and Follow-up (Visit 17). The clinician rates how much the subject's illness has improved or worsened relative to Visit 3 (Week 0). The Overall CGI-I score is rated on a 7-point scale, where 1='very much improved'; 2='much improved'; 3='minimally improved'; 4='no change'; 5='minimally worse'; 6='much worse'; 7='very much worse'. Scores of 1, 2, and 3 indicate improvement. Within subject change is indicated by the score at each relevant follow-up visit (Week 6, Visit 9 and Week 13, EOT, Visit 16). If an overall score is missing, that subject will be excluded from analysis at that visit.

Summary statistics for the CGI-I Overall score will be displayed at all post-baseline visits. Within subject changes will be analyzed using a Wilcoxon signed rank test at EOT and Week 6. The overall score will be presented in figures as described in Section 9.2. As this score is categorical, the waterfall plots will be adjusted so a score of "7 – Very Much Worse" will be presented at the bottom of the graph and a score of "1 – Very Much Improved" will be presented at the top of the graph. The overall score will also be presented as a line graph at post-baseline visits.

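### The stated CGI-I power (80/85/90%) fits a continuous outcome; with integer ratings and the exact test in Protocol 11.3 it is about 65/72/81% at n=10 and 73/78/85% at n=20

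*Protocol*

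**What the plan says.** Protocol 11.1, the synopsis and SAP 5.1 give the same sizing argument: within-participant change in CGI-I, SD about 0.7 at one timepoint, two-sided 0.05, Wilcoxon signed-rank test.

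- For n=10: "the study will be able to detect a difference of 0.87 units of change in the CGI-I at a power of 0.90", followed by "For a power of 0.80, 0.85, and 0.90, the detectable difference would be 0.75, 0.80, and 0.87 or larger, respectively". The matching effect sizes are given as 1.07, 1.14 and 1.24.
- For n=20: "For a power of 0.80, 0.85, and 0.90, the detectable difference would be 0.48, 0.51, and 0.55 or larger, respectively".
- For n=10 with SD 1.5: differences of 1.61, 1.71 and 1.86.

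Both sample sizes matter, because Protocol 7.1 adds: "Additional participants may be screened, enrolled, and treated to achieve approximately 20 study completers".

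On the analysis, Protocol 11.3 says: "A Wilcoxon signed rank test will be used to test for improvement and an exact significance level will be computed". The synopsis drops the word exact ("signed rank test will be used to test for improvement and a significance level will be computed"). SAP 9.2.1 says only: "Within subject changes will be analyzed using a Wilcoxon signed rank test at EOT and Week 6". Protocol 9.5.9.2 makes CGI-I a 7-point integer rating with 4 meaning no change. SAP 5.3 adds: "For the Clinical Global Impression Scale Improvement and Caregiver Impression of Change, change from Baseline is the value at the visit". Neither document states the null value for the CGI-I test.

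**The concern.** A signed-rank test on a short integer scale behaves differently from one on continuous data. Ratings equal to the null are discarded, and the remaining changes are heavily tied. With few non-zero changes the exact p-value moves in coarse steps and may be unable to reach 0.05. The sizing text allows for none of this.

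These detectable differences are the quantitative sizing rationale in all three places. If the power is lower than stated, a non-significant CGI-I result is weaker evidence against an effect than the plan implies. At n=10 and a true change of 0.75, the miss rate would be about 35% instead of 20%.

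The missing null is a related gap. Read literally, SAP 5.3 passes the raw rating to the test. Against zero, all ten ratings are positive and p = 2/2^10 = 0.002 whatever the drug does.

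**Working it through.** **Inputs.** From Protocol 11.1 and SAP 5.1: SD 0.7, two-sided 0.05, n of 10 and 20, differences 0.75/0.80/0.87 and 0.48/0.51/0.55. From Protocol 9.5.9.2: integer ratings 1 to 7. From Protocol 11.3: exact p-value. Assumed here: null of 4; tested quantity = 4 − rating, so values run from −3 to +3; 0.7 is the SD of the ratings themselves.

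**1. Reproduce the plan's figures.** On normal data the signed-rank test has efficiency 3/π relative to the t-test. That gives 10 × 3/π = 9.55 and 20 × 3/π = 19.10, rounded down to 9 and 19. One-sample t-test power with noncentrality (difference/0.7) × √n is then:

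| n used | differences | power |
|---|---|---|
| 9 | 0.75/0.80/0.87 | 80.3/85.0/90.2% |
| 19 | 0.48/0.51/0.55 | 80.7/85.1/89.9% |

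Solving at n=9 for 80/85/90% gives effect sizes 1.067/1.142/1.237, against the stated 1.07/1.14/1.24. The published figures are therefore those of a continuous normal outcome.

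**2. Is the exact test alone the cause?** No. Simulating it on continuous normal data gives 83.6/87.9/92.5% (n=10) and 80.9/85.3/90.1% (n=20).

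**3. Put the outcome on its integer scale.** Take a rounded normal whose rounded values have mean 0.75 and SD 0.7. The cell probabilities are about 2.5% at −1, 32.3% at 0, 53.3% at +1, 11.7% at +2 and 0.3% at +3. About a third of children are discarded and most of the rest tie at one point.

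Exact two-sided p-values when all changes are one point:

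- 5 of 5 improved: 2/2^5 = 0.0625
- 6 of 6 improved: 2/2^6 = 0.031
- 7 improved, 1 worse: 2 × (1+8)/2^8 = 0.070
- 8 improved, 1 worse: 2 × (1+9)/2^9 = 0.039

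Fewer than six non-zero changes cannot give p ≤ 0.05, and six to eight one-point changes must all agree. At n=10 the chance of fewer than six is 19/15/10% across the three differences; at n=20 it is under 1%.

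**4. Power by full enumeration of multinomial outcomes** (midranks, zeros dropped):

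| p-value method | n=10 | n=20 |
|---|---|---|
| Stated | 80/85/90% | 80/85/90% |
| Exact | 64.9/72.1/80.7% | 72.7/78.4/84.8% |
| Normal approximation, continuity-corrected | 77.2/82.5/88.4% | 80.1/84.8/89.8% |
| Normal approximation, uncorrected | 81.8/86.4/91.5% | 81.0/85.6/90.4% |

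Ranking the zeros before dropping them moves the exact powers by under 0.3 points.

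**5. Dependence on shape.** Over a grid of unimodal integer distributions with the same mean and SD, exact power is:

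- n=10: 62–76/65–81/70–89% (563/625/598 shapes, all below the stated power).
- n=20: 68–85/73–91/78–95% (329 shapes, of which 93/93/92% fall below).

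A separate search of extreme unimodal shapes lowered the floor at n=10, difference 0.87, to 69%.

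**6. Differences that restore 80/85/90%** (exact, rounded normal): 0.864/0.912/0.973 at n=10 and 0.519/0.551/0.591 at n=20. In SD terms at 80% power, this is like planning with 0.7 × 0.864/0.747 = 0.81 at n=10, or 0.7 × 0.519/0.476 = 0.76 at n=20, where 0.747 and 0.476 are the t-based detectable differences.

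**7. SD 1.5, n=10.** The exact test gives 73/77/82%. Matching that SD and mean on this scale puts 40–51% of children at the best rating, so the row is hard to interpret.

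**The case against.** The stated figures are not miscalculated: they are right for a continuous normal outcome, and the fault is an unstated assumption. That is fair, and calling the assumption continuous is an inference from what reproduces the numbers.

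The shortfall also needs both integer data and an exact p-value, and the word exact appears only in Protocol 11.3. An uncorrected normal approximation restores the stated power under a rounded normal, with two-sided size of 4.7% (n=10) and 4.2% (n=20). This stands as a condition on the finding. The SAP governs where it and the Protocol are inconsistent, but SAP silence on the p-value is not an inconsistency. Protocol 11.3 is the only method either document states.

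Shape matters too. At n=10 and 0.87 the most favourable unimodal shape reaches 89.1%, almost no loss, and a contrived gapped shape reaches 92%. Other gapped shapes go as low as 58%. So the n=10 result holds for plausible shapes, not every conceivable one.

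Protocol 11.1 warns that a larger SD would raise the detectable differences. That does not cover this loss, which occurs at SD 0.7.

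Finally, the stakes are low. The primary objective is safety, tolerability and PK. SAP 9.1 has no primary efficacy endpoint, SAP 5 calls the tests descriptive, and SAP 2.2 reports that nobody enrolled under Protocol version 3.0. All of that stands and limits the point to planning text and interpretation. Reading SAP 5.3 as a test against zero is uncharitable, since SAP 9.2.1 labels 4 as no change, but the null still needs writing down.

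**Conclusion.** The concern holds. Under the analysis as written, the power attached to the stated differences is about 15/13/9 points too high at n=10 and 7/7/5 points too high at n=20.

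This rests on a null of 4, an exact p-value, 0.7 as the SD of the integer ratings, and a rounded-normal shape. If 0.7 is instead a latent SD before rounding, power is lower again: 58/65/75% at n=10 and 66/72/79% at n=20. The n=20 shortfall can vanish under favourable shapes.

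Confidence is medium, because the central figures depend on distribution and p-value method. The correction should be made, but it does not affect the primary objective.

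**What to change.** 1. In the SAP, state that CGI-I is tested against 4 and that the p-value is exact, as in Protocol 11.3.
2. In Protocol 11.1, the synopsis and SAP 5.1, name the assumed distribution and restate one of the following, labelled as shape-dependent:
   - detectable differences of about 0.86/0.91/0.97 (n=10) and 0.52/0.55/0.59 (n=20) for 80/85/90% power; or
   - the existing differences with powers of about 65/72/81% and 73/78/85%, plus the ranges in step 5 of the working.
3. Recompute or delete the SD 1.5 row.
4. If an approximate p-value is intended, name it, say whether it is continuity-corrected, and remove exact from Protocol 11.3. Uncorrected, the SD 0.7 figures roughly hold under a rounded normal. Corrected, the n=20 figures roughly hold, but n=10 still needs restating (77/82/88%, or differences of about 0.78/0.83/0.89).

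The cost is a text change in three places plus one SAP sentence. On the exact route the detectable differences rise by 0.10 to 0.11 units at n=10 (0.86 − 0.75 = 0.11; 0.97 − 0.87 = 0.10) and by 0.04 at n=20 (0.52 − 0.48). No extra participants are needed.
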